9.3 Analysis Populations

Analysis populations are Randomized participant, mITT, Per-Protocol (PP), and the Safety population (all participants receiving any dose of treatment), the Per Protocol population (received drug and had no major documented protocol violations), defined as in

Table 3.

Table 3 Populations for Analysis

Population	Description
Randomized	All participants randomized regardless of adherence to treatment or study status, analyzed as randomized.
mITT	All participants in the Randomized population who received at least one dose of the test article (NONS or placebo), analyzed as randomized.
Daily Use	All participants in the mITT set who documented at least one self-administered NONS dose per day on at least 25 of 28 expected dosing days or 90% of days while on study treatment. Analyzed as treated
Per Protocol	All participants in the mITT set who documented self-administered NONS on at least 25 of 28 expected dosing days or 90% of days and 80% of expected doses while on study treatment. Analyzed as treated.
Safety	All randomized participants who receive at least 1 dose of the study intervention.

Abbreviations: mITT=modified intent-to-treat; NONS=nitric oxide nasal spray.

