6.6.5 Early Termination Assessment

Participants that discontinue the study early due to COVID-19 infection or are hospitalized for any reason are encouraged to attend the early termination assessment to the best of their ability. If the participant is unable to complete the treatment diary or attend the early termination assessment, the designated emergency contact is encouraged to submit this information on behalf of the participant to the best of their ability.

Protocol deviations to be recorded for this study include visit/phone/telehealth procedure deviations and noncompliance; PRO noncompliance; study medication dosing noncompliance; and dispensing deviations. A special emphasis will be placed on dosing errors, lack of completion of the required daily PRO reporting, and the incomplete return of study medication at the conclusion of the study.

Study medication noncompliance is defined as less than 80% of expected doses administered while on possible study treatment. PRO noncompliance is defined as less than 70% of possible reporting days of data recorded, eg. before a hospitalization, or an early termination.

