7.12.1 Removal of Participants from the Trial or Study Treatment

The Investigator may withdraw a participant from the study for any of the following reasons:

- A protocol violation occurs,
- A serious or intolerable adverse event occurs,
- A clinically significant change in a laboratory parameter occurs,
- The Sponsor or Investigator terminates the study, or
- The participant requests to be discontinued from the study.

A participant may choose to discontinue study treatment and/or withdraw from the study at any time. Participants who become pregnant during the study are to be withdrawn from study treatment. In the absence of a medical contraindication, every effort should be made by the Investigator to encourage participants who prematurely discontinue treatment to remain in the study as appropriate and, at a minimum, follow the participant for safety data collection.

7.12.1.1 **Discontinuation from Study Drug Treatment**

Participants may discontinue for the following reasons: any study drug related AEs that in the opinion of the Investigator, makes it unsafe for the participant to continue; any study drug related AE that repeats upon re-challenge.

A participant may be discontinued prematurely from study drug treatment for the following reasons:

- AE (including hospitalization for COVID-19/sequalae)
- Withdrawal by participant (specify reason in the eCRF)
- Lost to Follow-up
- Pregnancy

- Physician decision (ie, Investigator decision specify reason in the eCRF)
- Sponsor decision (specify reason in the eCRF)
- Noncompliance with study protocol
- Other (specify reason in the eCRF)

7.12.1.2 **Discontinuation from Study**

A participant may be discontinued prematurely from the study (in its entirety) for the following reasons:

- AE (including hospitalization for COVID-19/sequalae)
- Withdrawal by participant (specify reason in the eCRF)
- Lost to Follow-up
- Death
- Physician decision (ie, Investigator decision specify reason in the eCRF)
- Sponsor decision (specify reason in the eCRF)
- Noncompliance with study protocol
- Other (specify reason in the eCRF)

If a participant is withdrawn because of an adverse experience, the participant will be followed and treated by their health care provider (with documented follow-up) until the abnormal parameter or symptom has resolved or stabilized.

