9.5 Analysis of Efficacy

9.5.1 Primary Efficacy Analysis

The primary efficacy objective is to demonstrate that NONS product reduces the risk of COVID-19 infection. The associated null hypothesis is that the hazard ratio (HR) of NONS relative to placebo is greater than 1, or H_0 : $HR \ge 1$, or equivalently in terms of a vaccine efficacy, H_0 : $VE \ge 0$ where vaccine efficacy is calculated as VE = 100% x (1-HR). The HR will be estimated using a Cox proportional hazard regression model with a fixed effect only for treatment arm. Due to the small, expected event rate (see the Section 9.2), incorporation of additional fixed effects may not be possible. However, as a sensitivity analysis, a stratified Cox model using randomization strata (≥ 65 , <65 at increased risk, < not at increased risk) will also be fit. Similarly, age-group (\ge /<65) and region-specific models will be fit, aggregating adjacent provinces, states, or larger geographies to enable model convergence and evaluate, to the extent possible, whether differences exist.

The primary analysis will be executed in the mITT data set and count all cases occurring starting from the day after participants begin administering study treatment.

For all models, a 2-sided score-based 95% confidence interval (CI) and 2-sided p-value for the effect of NONS will be calculated.

The estimand of the primary analysis is a treatment policy strategy and will consider intercurrent events as censored. Specifically, participants who stop administering NONS for any reason, stop submitting data to the electronic patient-reported outcomes (ePRO) system, do not submit paper diaries, or are unreachable by telephone contact, will be censored on the day of their last ePRO clinical status submission or last available documented day on paper diary (ie, the last day confirming no positive COVID-19 test). Participants who submit COVID-19 test results following Day 28, will be censored at Day 28. Participants submitting a COVID-19 test result on or prior to Day 28 will be considered to have reached the primary endpoint on the day that the specimen (ie, nasal swab) is collected, not the date of the test. Positive test results obtained within 48 hours of randomization will be considered infected at randomization and not counted as events.

The Cox model will be fit to the following sets (if different) as sensitivity analyses:

- mITT set counting all cases after randomization,
- PP set counting cases after first administration,

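### The Per Protocol rule sets no minimum time on treatment, so a one-day user can qualify and may add off-spray follow-up to two sensitivity analyses

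*Combined protocol and SAP*

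**What the plan says.** Table 3 (Section 9.3) admits to the Per Protocol set members of the mITT set who documented dosing on 25 or more of the 28 days, "or 90% of days and 80% of expected doses while on study treatment". The Daily Use set has the same structure without a dose percentage: "at least one self-administered NONS dose per day on at least 25 of 28 expected dosing days or 90% of days while on study treatment". Neither row states a minimum time on treatment.

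The text above the table describes Per Protocol differently, as participants who "received drug and had no major documented protocol violations", without saying whether early stopping is such a violation. Section 6.6.5 adds a deviation rule: "Study medication noncompliance is defined as less than 80% of expected doses administered while on possible study treatment".

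Under Section 9.5.1, participants who stop NONS for any reason are among those who "will be censored on the day of their last ePRO clinical status submission or last available documented day on paper diary". Section 7.12.1 asks investigators "to encourage participants who prematurely discontinue treatment to remain in the study", and the Schedule of Events runs daily reporting over Days 1 to 35. Section 9.5.1 uses the Per Protocol set in two sensitivity Cox models, one counting cases from first administration and one from randomization. It lists no analysis of the Daily Use set.

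**The concern.** A Per Protocol analysis is meant to show the effect among people who used the spray as intended. A rule that divides by days on treatment, with no minimum, cannot tell a participant who sprayed for 28 days from one who sprayed for one. If the second keeps reporting, the follow-up is almost all off spray but is analyzed as adherent time. In the NONS arm this pulls the hazard ratio toward 1.

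A second, smaller feature concerns cases. If treatment ends at the positive test, the event itself shortens the denominator, so a case is allowed fewer missed days than a non-case who completes the course. Membership then depends partly on the outcome.

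What is at stake is how the two Per Protocol models are read beside the primary result, with about 12 events expected in the whole trial.

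**Working it through.** **1. The plan's own figure.** Inputs from Section 9.2: hazard ratio 0.15, two-sided 0.05, 90% power, 1:1, 11,480 in mITT (5,740 per arm), placebo rate 0.000075 per day, loss 1.05% per day.
- Events (Schoenfeld): 4 × (1.960 + 1.282)² / (ln 0.15)² = 11.68, rounded up to 12.
- Expected events per arm: 5,740 × λ/(λ + 0.0105) × (1 − exp(−28(λ + 0.0105))). With λ = 0.000075 this is 10.43 on placebo. With λ = 0.15 × 0.000075 it is 1.57 on NONS. The total is 12.00.

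The stated 2 + 10 events and 11,480 participants are reproduced. Nothing below alters them.

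**2. When the percentage route matters.** 90% of 28 is 25.2, so 26 whole days. A completer who fails 25 of 28 also fails 90%. The route changes membership only when the treatment period is shorter than 28 days.

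**3. The one-day user.**
- Three doses on Day 1, then stop: days 1/1 = 100%, doses 3/3 = 100%. Qualifies for Per Protocol and Daily Use, however the *and* and *or* are grouped.
- Two doses on Day 1: 2/3 = 67%. Fails Per Protocol, qualifies for Daily Use.
- Against the full course the first person has 1/28 days and 3/84 doses, both 3.6%.

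**4. Effect of off-spray time.** Assumptions: a share q of the NONS arm stops but reports to Day 28; the hazard ratio is 0.15 on spray and 1 off spray; the hazard is constant; stopping in the placebo arm changes nothing. With w the off-spray share of NONS person-time, the observed hazard ratio is about 0.15(1 − w) + w.
- *All stop after Day 5:* w = q × 23/28.
- *Stopping spread over the course:* daily stop probability s = 1 − (1 − q)^(1/28), and w = 1 − [Σ(1 − s)^(k−1), k = 1 to 28]/28.

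| q | w, spread | HR, spread | w, Day 5 | HR, Day 5 |
|---|---|---|---|---|
| 5% | 2.4% | 0.171 | 4.1% | 0.185 |
| 10% | 4.9% | 0.192 | 8.2% | 0.220 |
| 25% | 12.7% | 0.258 | 20.5% | 0.325 |

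Efficacy would read about 83%, 81% or 74% (spread) and 82%, 78% or 68% (Day 5), against a true 85%.

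**5. Cases and missed days.** Assume treatment ends on the day of the positive specimen.
- With d treatment days, one wholly missed day gives (d − 1)/d. That is below 90% for d = 2 to 9 (8/9 = 88.9%) and equals 90% at d = 10. A completer may miss 3 days.
- At an assumed 5% daily chance of a missed day, the share kept is 95.1% of 28-day non-cases (at most 3 of 28 missed), 69.8% of Day 7 cases (0 of 7 missed) and 83.3% of cases spread evenly over Days 2 to 28.
- Days 2 to 9 hold 8/27 = 30% of Day 2 to 28 cases with no loss, or 33% with 1.05% daily loss. That is about 4 of 12, of which only those with a missed day would be dropped.
- If the miss rate is the same in both arms, cases are dropped in the same proportion in each arm on each day, so retained events stay in the ratio 0.15. Events are lost; the hazard ratio is not biased.

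**The case against.** The strongest reply is that the plan already deals with early stoppers. The wording above Table 3, "received drug and had no major documented protocol violations", could exclude them. If the treatment in Section 6.6.5 that is called possible means the whole 28-day course, a one-day user with 3/84 doses is noncompliant. Section 9.5.1 names stopping NONS as a reason for censoring. Sections 5.9 and 7.12.1 let the investigator terminate participants who do not confirm use or do not comply, and the encouragement to stay is qualified and has safety data as its minimum. Sections 9.1 and 9.5.1 also leave detail to a separate SAP.

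Part of this stands. These passages might be applied so that little off-spray time enters, and the censoring rule is written for the primary analysis, so its use in the Per Protocol models is only implied. But none of them settles the matter. The terms major and possible are not defined, Table 3 gives a different and explicit rule, and the censoring date is the last status report.

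Four stronger readings are tempting and not supported:
- *That adherence is judged only over time on treatment.* The 25-of-28 route uses the full course. The trouble is that the *or* lets a stopper bypass it.
- *That the plan's 25% censoring makes the 25% scenario likely.* That figure describes people who leave follow-up, not people who stop spraying and keep reporting.
- *That dropping early cases distorts the hazard ratio.* With equal adherence between arms it does not. Treatment ending at the positive test is also an assumption: Section 3.3 only encourages early termination assessments. The 95% comparator takes non-cases who complete 28 days; with the plan's daily loss it is about 92%.
- *That the Daily Use results are compromised.* No efficacy analysis of that set is listed.

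**Conclusion.** The Per Protocol rule is faulty as written, and the fault is confined to supportive analyses. Its percentage route has effect only for shortened treatment and there admits one-day users. If the Section 9.5.1 censoring date applies to the Per Protocol models and stoppers keep reporting, the set includes off-spray time. Under the assumptions shown, the hazard ratio moves from 0.15 to between 0.17 and 0.325. The upper end needs a quarter of the NONS arm to stop on Day 5, report throughout and lose protection at once. The documents give no figure for how many participants would stop and keep reporting.

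The outcome-dependent allowance for missed days is a secondary flaw. It can cost some of the roughly 12 expected events, but it does not bias the estimate when adherence is equal between arms. The definition should be corrected before unblinding. The mITT primary analysis and the sample size are unaffected.

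**What to change.** In Table 3, measure Per Protocol adherence from first dose to the earliest of first positive specimen, Day 28 or last status report. Count days after stopping as missed. Require at most 3 missed days and at least 80% of expected doses in that window. State how this relates to "received drug and had no major documented protocol violations", so that one definition remains.

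Checks on this rule:
- A participant who stops after Day 5 and reports to Day 28 has 23 missed days and is out.
- A one-day user who reports to Day 2 has 3/6 = 50% of doses and is out.
- Any stopper who remains adds at most 3 off-spray days.
- At the same 5% daily miss chance, about 96% of cases over Days 2 to 28 and 95% of 28-day non-cases are kept, so the gap by outcome largely closes.
- It does not close fully: one wholly missed day still removes a case on Days 2 to 4, because 1/2, 2/3 and 3/4 are below 80%.

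A 28-day denominator for everyone would not serve, since it would drop every case whose treatment ends before 25 dosed days.

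Apply the same window to Daily Use for consistency. Having no dose requirement, that set would still admit a one-day user whose last report is on Day 4 (3 missed days).

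The cost is two lines in Table 3 and a somewhat smaller Per Protocol set.

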9.4 Demographics and Baseline Characteristics

Demographic data will be provided in listings and summary tables with descriptive statistics. No statistical hypothesis tests will be performed on these characteristics.

9.5 Analysis of Efficacy

9.5.1 Primary Efficacy Analysis

The primary efficacy objective is to demonstrate that NONS product reduces the risk of COVID-19 infection. The associated null hypothesis is that the hazard ratio (HR) of NONS relative to placebo is greater than 1, or H_0 : $HR \ge 1$, or equivalently in terms of a vaccine efficacy, H_0 : $VE \ge 0$ where vaccine efficacy is calculated as VE = 100% x (1-HR). The HR will be estimated using a Cox proportional hazard regression model with a fixed effect only for treatment arm. Due to the small, expected event rate (see the Section 9.2), incorporation of additional fixed effects may not be possible. However, as a sensitivity analysis, a stratified Cox model using randomization strata (≥ 65 , <65 at increased risk, < not at increased risk) will also be fit. Similarly, age-group (\ge /<65) and region-specific models will be fit, aggregating adjacent provinces, states, or larger geographies to enable model convergence and evaluate, to the extent possible, whether differences exist.

The primary analysis will be executed in the mITT data set and count all cases occurring starting from the day after participants begin administering study treatment.

For all models, a 2-sided score-based 95% confidence interval (CI) and 2-sided p-value for the effect of NONS will be calculated.

The estimand of the primary analysis is a treatment policy strategy and will consider intercurrent events as censored. Specifically, participants who stop administering NONS for any reason, stop submitting data to the electronic patient-reported outcomes (ePRO) system, do not submit paper diaries, or are unreachable by telephone contact, will be censored on the day of their last ePRO clinical status submission or last available documented day on paper diary (ie, the last day confirming no positive COVID-19 test). Participants who submit COVID-19 test results following Day 28, will be censored at Day 28. Participants submitting a COVID-19 test result on or prior to Day 28 will be considered to have reached the primary endpoint on the day that the specimen (ie, nasal swab) is collected, not the date of the test. Positive test results obtained within 48 hours of randomization will be considered infected at randomization and not counted as events.

The Cox model will be fit to the following sets (if different) as sensitivity analyses:

- mITT set counting all cases after randomization,
- PP set counting cases after first administration,
- PP set counting all cases after randomization, and
- Randomized set counting all cases after randomization

The primary analysis will be repeated in the following subgroups:

- Subjects unvaccinated against SARS-CoV-2 prior to randomization
- Subjects partially vaccinated against SARS-CoV-2 prior to randomization
- Subjects fully vaccinated against SARS-CoV-2 prior to randomization
- Subjects who are fully vaccinated and have received a booster shot against SARS-CoV-2 prior to randomization
- Subjects who become partially vaccinated against SARS-CoV-2 during the course of the study
- Subjects who become fully vaccinated against SARS-CoV-2 during the course of the study
- Subjects who receive a booster vaccine against SARS-CoV-2 during the course of the study

Specific procedures to account for missing data, unused or spurious data and criteria for termination will be delineated in the SAP. Procedures for reporting any deviation(s) from the original statistical plan will be described in the SAP and justified (if needed) in the final clinical study report.

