5.4 Method of Assigning Participants to Treatment Groups

Participants will be randomized 1:1 to receive either NONS or placebo. Randomization will be in a double-blinded manner using an IWRS with pre-generated randomization lists. When participants performing remote visits (only) are confirmed as eligible, the IWRS system will provide the participant's contact information and randomized assignment to the regional drug distribution center who will compile the kit with the appropriate 3 bottles of test articles (NONS or placebo) and ship them directly to the participant.

Participants may only enroll on the study once. During eligibility screening, data will be collected verifying identity (date of birth and partial postcode) to prevent participants from attempting to enroll the study again.

Randomization will be stratified based on age and COVID-19 risk factors. There will be three strata:

- 1. \geq 65 years of age
- 2. < 65 years of age and at increased risk
- 3. < 65 years of age and not at increased risk

Participants will be considered 'at increased risk' if they report having at least one of the following risk factors during Screening:

- Cancer
- Chronic lung disease (eg: emphysema and chronic bronchitis, idiopathic pulmonary fibrosis and cystic fibrosis) or moderate to severe asthma
- Significant cardiac disease (eg: heart failure, coronary artery disease, congenital heart disease, cardiomyopathies, and pulmonary hypertension)
- Down Syndrome
- Immunocompromised following immunosuppressive therapies (e.g. post-transplant procedures, chemotherapies, treatments with biologics/biosimilars)
- COPD (chronic obstructive pulmonary disease)
- Obesity (body mass index $[BMI] \ge 30 \text{ kg/m}^2$)
- Diabetes (Type 1, Type 2 or gestational)
- Liver disease
- HIV infection

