5.5 Blinding

Following confirmation of eligibility and baseline data collection, participants will be enrolled and randomized.

If an in-person on-site visit is performed, blinded kits will be delivered to, or prepared at, the sites. A subject number will be assigned to each randomized participant. Site staff/physician will then dispense kit labeled with the authorization number generated during randomization to the individual participant.

For participants performing remote visits, each authorization number/code will be associated with a specific treatment assignment, within stratum, from a pre-generated list. The authorization number/code will be provided to the regional study drug distribution center(s) who will select the appropriate treatment assignment, compile a blinded kit, and distribute directly to the participant. In addition to the necessary staff at the study drug distribution center, unblinded staff at the study contract research organization (CRO) will be the only study personnel with access to unblinded treatment assignments.

If the Investigator, or any medical caregiver, determines that unblinding is warranted to manage a medical condition, AE, or other purpose, they should follow the specified contact

procedure in the study Safety Monitoring Plan – contact information will be available to study participants to provide to physicians or other medical caregivers who may be providing care to the subject. Safety must always be the first consideration in making a determination to unmask. The requestor should believe that knowledge of the participant's randomized study treatment would influence the participant's care or their treatment decisions. Upon approval by the Sponsor, or in the case of urgent medical need, the unblinding information will be provided with notification to the Sponsor and documentation of the unblinding event in the study file.

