9.2 Determination of Sample Size

For an annualized infection rate of 3% in the placebo arm (daily incidence = 0.000075), and assuming a true hazard ratio of 0.15 implying protective effect of NONS equivalent to a vaccine efficacy of 85%, a sample size of 11,480 participants randomized 1:1 (NONS:Placebo) and available in the modified intent-to-treat (mITT) population will provide 90% power to demonstrate superiority of NONS to placebo in preventing COVID-19 infections reported through 28 days, based on Cox regression model and a 2-sided 0.05-level test (Schoenfeld 1983). The expected number of events in the two arms is 2 and 10 for the NONS and placebo groups respectively. This further assumes 25% censoring during the 28-day period (1.05% loss per day).

Sample size calculations conducted under version 1.0 of the protocol (dated April 27, 2021) used estimates of annualized case rates as listed in Table 2. At that time, the recent estimated annualized infection rate based on confirmed cases ranged from 2.2 through 3.9% in select Canadian provinces, though there was considerable variability, and these rates underestimate the true infection rates considering those untested. The US and other nations may have substantially higher infection rates and require fewer subjects to be randomized.

In particular, for the Czech Republic, Slovakia, and Sri Lanka, the reported annualized rates are between 0.14% and 8.23%, 0.07% and 7.27%, and 1.48% and 6.18% respectively over the period of May 1, 2021, to July 31, 2021. We are therefore likely to have sufficient power to conduct this study in those countries.

The maximum number of participants who will be randomized is 13,000, in order to achieve a maximum of 11,480 participants initiating their randomized treatment assignment and entering the mITT population. If the infection rate is higher than assumed here, enrollment and randomization will be closed if the total number of COVID-19 events in the mITT population exceeds 18 cases, 50% more than the number expected for 90% power. This inflation accounts for the increased infection rate and the consequent increased risk of infection between the time of randomization and time of initiation of study treatment due shipping times.

Table 2 Daily COVID-19 Counts

Population	Estimated annualized rate in February 2021	Equivalent date based on study in control arm	assumption	Days Daily Confirmed case counts exceeded 3% / 4% annualized rate		

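### Make the Cox model stratified by the three randomisation strata the primary model; the few-events reason for a treatment-only model does not bear on stratification (optional consistency fix)

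*Combined protocol and SAP*

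**What the plan says.** On design, section 5.4 states: "Randomization will be stratified based on age and COVID-19 risk factors". The three strata are age 65 or over, under 65 at increased risk, and under 65 not at increased risk. For remote participants, section 5.5 adds that "each authorization number/code will be associated with a specific treatment assignment, within stratum, from a pre-generated list".

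On analysis, section 9.5.1 (repeated in the synopsis) says: "The HR will be estimated using a Cox proportional hazard regression model with a fixed effect only for treatment arm". The reason offered is that, with so few events expected, "incorporation of additional fixed effects may not be possible". The next sentence brings the strata back: "However, as a sensitivity analysis, a stratified Cox model using randomization strata". A score-based interval and p-value are required for every model. Section 9.5.2 analyses the secondary endpoint in the same way as the primary, so it inherits the treatment-only model.

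**The concern.** The primary model decides whether the trial succeeds, and it does not condition on the groups within which treatment was allocated. The only reason given concerns extra model coefficients, and a stratified Cox model has none: it keeps the single treatment coefficient and lets each stratum have its own baseline hazard.

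Two things are at stake. The first is consistency between design and analysis in a trial expected to yield about 12 events, where it should be settled beforehand which of two near-identical tests counts. The second is robustness. Section 9.5.1 censors people who stop treatment or stop reporting, and section 9.2 plans for 25% censoring. If dropout differed by stratum and also by arm, the stratum mix of the two arms' risk sets would drift apart over the 28 days. The unstratified HR would then pick up differences in infection risk between strata.

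**Working it through.** **1. The plan's own figures.** Inputs from section 9.2: placebo hazard 0.000075 per day, HR 0.15, loss 1.05% per day, 28 days, 11,480 participants allocated 1:1, 2-sided 0.05, 90% power.

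- Schoenfeld events: 4 × (1.960 + 1.282)² / (ln 0.15)² = 11.68, rounded up to 12. Power with 12 events: Φ(√12 × 1.897/2 − 1.960) = 90.8%.
- Expected events per arm, with c = −ln(1 − 0.0105) = 0.01056: 5,740 × λ/(λ + c) × [1 − exp(−28(λ + c))]. This gives 10.43 on placebo (λ = 0.000075) and 1.57 on NONS (λ = 0.15 × 0.000075), 11.99 in total.

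The stated 10 and 2 events and the 90% power reproduce. With 1:1 allocation in each stratum, the same formula gives the same N and events for the stratified model.

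**2. Can the stratified model be fitted with about 12 events?** Both models solve one equation in one unknown β: Σ over events of [A − n₁e^β/(n₁e^β + n₀)] = 0, where A is 1 for a NONS event and n₁, n₀ are the numbers at risk on NONS and placebo. The unstratified model counts everyone at risk; the stratified model counts only the event's own stratum. A stratum without events contributes nothing. The estimate fails only when one arm has no events, which affects both models alike. For NONS that probability is about exp(−1.57) = 21%.

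**3. Balanced dropout.** Simulation of 11,480 participants with 1:1 allocation within strata, 1,500 trials per row. Stratum shares and relative hazards are assumptions, in the order of section 5.4, because the documents give none.

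| Shares; hazards | True HR | Rejects, unstratified | Rejects, stratified | HR not estimable (both models) |
|---|---|---|---|---|
| 10/30/60%; 3:2:1 | 0.15 | 77.9% | 77.8% | 21.1% |
| 10/30/60%; 3:2:1 | 1 | 4.8% | 4.9% | 0% |
| 5/15/80%; 1:3:5 | 0.15 | 76.8% | 76.9% | 22.7% |
| 5/15/80%; 1:3:5 | 1 | 4.7% | 4.7% | 0% |

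The two tests disagreed in at most 0.13% of trials, and the largest difference in log HR was 0.035. That simulated power is 77% to 78% rather than 90% is a small-sample matter common to both models and is not part of this point.

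**4. Dropout that differs by stratum and arm.** Assume shares 10/30/60%, a true HR of 1.00, and NONS dropout in the first two strata at 2 or 3 times the planned rate. All other groups drop out at the planned rate, and dropout is independent of infection within each stratum and arm.

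Illustration at Day 14, 3 times the rate, hazards 3:2:1. The proportion remaining is exp(−14c) = 0.863, or exp(−42c) = 0.642 in the affected strata. The NONS mix becomes 8.3/24.9/66.8%, with mean relative hazard 3(0.083) + 2(0.249) + 0.668 = 1.414. Placebo stays at about 0.3 + 0.6 + 0.6 = 1.5. The ratio at that day is 0.943.

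Integrating over 28 days and solving the equation in step 2 gives:

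| Hazards | Unstratified HR, 2 times | Unstratified HR, 3 times |
|---|---|---|
| 3:2:1 | 0.97 | 0.95 |
| 1.5:1.25:1 | 0.99 | 0.98 |
| 1:1:1 | 1.00 | 1.00 |
| 1:2:3 | 1.02 | 1.03 |

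The stratified HR is 1.00 throughout, by construction of the within-stratum assumption.

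**5. Scale.** With hazards 3:2:1 the shift is ln 0.973 = −0.028 and ln 0.948 = −0.054, against a standard error of log HR of about 0.45: 0.06 and 0.12 standard errors. Two-sided type I error moves from 5.0% to 5.04% and 5.16%, and the tail favouring NONS from 2.5% to 2.9% and 3.3%.

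**The case against.** The strongest reply is that nothing is missing. The stratified model is pre-specified with its own score-based interval and p-value, so both results will be reported, and the change only exchanges two labels. The plan also never says that few events rule out stratification: it doubts further fixed effects and then goes on to plan the stratified fit. Both points stand. They limit the weight of the point, but they also leave the plan with no reason for keeping the stratified model out of the primary position.

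A reader might infer that the primary HR is biased. The documents do not support that. They give no stratum sizes, no infection risk by stratum and no expected dropout by arm, so even the sign of any drift is unknown. The scenarios in step 4 are also severe: 2 and 3 times the planned rate mean about 45% and 59% lost by Day 28 in the affected NONS strata, against about 26% elsewhere, in a double-blind saline-controlled trial.

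A reader might equally infer that the stratified HR is unbiased. That needs censoring to be independent of infection risk within each stratum. Section 9.5.1 censors at stopping treatment or reporting, which could be informative within strata, and three coarse strata would not correct that.

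**Conclusion.** The point holds as an optional consistency fix. Treatment is allocated within three strata, the primary model does not use them, and the one reason given does not bear on stratification. With balanced dropout the choice makes practically no difference to power, type I error or the HR. If dropout differs by both stratum and arm, stratification removes the between-stratum drift: a few percent in the HR under the assumed shares, hazards and dropout multiples, in either direction, and zero if the strata have equal infection risk. This is not a finding that the planned primary test is invalid or underpowered because of the missing strata.

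**What to change.** In section 9.5.1 and the synopsis, name the Cox model stratified by the three randomisation strata as the primary model, with the score test and score-based confidence interval from that model, and keep the unstratified model as the sensitivity analysis. State that section 9.5.2 follows the same model, and carry the wording into the separate statistical analysis plan that section 9.1 announces.

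The cost is wording only: no change to sample size, number of events or data collected. Both models are already planned; the documents do not say whether either has been programmed.
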